**Table 6-1 Clinical Laboratory Parameters**

Category	Parameter
Chemistry	Sodium, potassium, chloride, bicarbonate, glucose, blood urea nitrogen, creatinine, total bilirubin, alkaline phosphatase, aspartate aminotransferase, alanine aminotransferase, lactate dehydrogenase, creatine kinase, total protein, albumin, calcium, phosphorus, uric acid, total cholesterol. The estimated glomerular filtration rate will be calculated by the central laboratory.
Hematology	Hemoglobin; hematocrit; red blood cell count; red blood cell indices (mean corpuscular volume, mean corpuscular hemoglobin, mean corpuscular hemoglobin concentration); white blood cell count, including differential (neutrophils, lymphocytes, monocytes, eosinophils, and basophils); platelet count
Urinalysis	Urine dipstick for specific gravity, pH, protein, glucose, ketones, bilirubin, and blood; microscopic examination including red blood cells/high-power field, white blood cells/high-power field, and casts/low-power field.
Coagulation	International Normalized Ratio
Serology	At Visit 1 only: anti-hepatitis A IgM antibody, hepatitis B surface antigen, anti-hepatitis C antibody, or anti-hepatitis E IgM antibody.
Urine Drug Screen	Screening for drugs of abuse (eg, marijuana, cocaine, phencyclidine, amphetamines, benzodiazepines, barbiturates, opiates) will be conducted using a urine drug screen at Visit 1. Urine drug screens positive for recreational (including marijuana regardless of legality) or illicit drugs or non-disclosed concomitant medications are not allowed to be repeated. All other positive urine drug screens may be repeated with permission from Allergan; a negative result or an explanation of a positive result due to concomitant medication use (eg, opioids prescribed for migraine pain) will be required for randomization.

A central laboratory will be used to evaluate all urine and blood samples, which will be collected, processed, and stored according to the instructions provided by the laboratory.

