11.2 Clinical Laboratory Assessments

Descriptive statistics for clinical laboratory values (in SI units) at baseline, postbaseline, and changes from baseline values at each postbaseline timepoint will be presented by treatment group for the following laboratory parameters:

Hematology: Hemoglobin, hematocrit, red blood cell count, red blood cell

indices (mean corpuscular volume, mean corpuscular hemoglobin, mean corpuscular hemoglobin concentration), white blood cell count, including differential (neutrophils, lymphocytes, monocytes, eosinophils, and basophils),

platelet count

Chemistry: Sodium, potassium, chloride, bicarbonate, glucose, blood

urea nitrogen, creatinine, total bilirubin, alkaline phosphatase, aspartate aminotransferase, alanine

aminotransferase, lactate dehydrogenase, creatine kinase, total protein, albumin, calcium, phosphorus, uric acid, total

cholesterol, eGFR

Urinalysis: Specific gravity, pH

In addition, descriptive statistics for values and changes from the baseline values in conventional units at each assessment time point will be presented for selected clinical laboratory parameters

SAP 3101-301-002 AGN-241689

listed in Appendix I. A description of reporting the lab values in conventional units in patient narratives (along with the standard reporting in SI units) is presented at the end of Appendix I.

Clinical laboratory test values will be considered potentially clinically significant (PCS) if they meet either the lower-limit or higher-limit PCS criteria listed in Table 11–1. The normal range for eGFR was not collected in the lab. Therefore, eGFR<60 mL/min/1.73m² is defined in Table 11–2 to classify renal function as the category of "Moderate eGFR Decrease or Worse" based on FDA guidance on PK studies in Patients with impaired renal function. The number and percentage of participants who have PCS postbaseline clinical laboratory values will be tabulated by treatment group. The percentages will be calculated relative to the number of participants with available non-PCS baseline values and at least 1 postbaseline assessment for the double-blind treatment period. The numerator will be the total number of participants with available non-PCS baseline values and at least 1 PCS postbaseline value during the study. A supportive tabular display of participants with PCS postbaseline values will be provided, including the PID number, baseline and all postbaseline (including non-PCS) values.

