In addition, a tabular display showing all AEs that occurred in participants who had PCS postbaseline clinical laboratory values will be provided.

Shift tables from baseline to end of the double-blind treatment period for clinical laboratory parameters will be presented by treatment group for the following categories: low, normal, and high, which are provided by the laboratory vendor.

Potential Hy's Law criteria within a 24-hour window is defined by a post baseline elevation of alanine aminotransferase (ALT) or aspartate aminotransferase (AST) ≥ 3 x ULN, along with total bilirubin (TBL) ≥ 2 x ULN and a non-elevated alkaline phosphatase (ALP) < 2 x ULN, all based on blood draws collected within a 24-hour period. Potential Hy's Law criteria without time window is defined by maximum of post baseline elevation of ALT or AST ≥ 3 x ULN, along with maximum of post baseline elevation of TBL ≥ 2 x ULN. Patients who meet the potential Hy's Law criteria from the first dose of study drug to the end of study will be summarized. Supportive tabular displays will also be provided.

Table 11–1 Criteria for Potentially Clinically Significant Laboratory Values

			PCS (Criteria
Category	Parameter	SI Unit	PCS Low	PCS High
Chemistry	Albumin	g/L	< 0.8 × LLN	> 1.2 × ULN
	Alanine aminotransferase	U/L		\geq 3.0 × ULN
	Alkaline phosphatase	U/L	_	\geq 3.0 × ULN
	Aspartate aminotransferase	U/L	_	\geq 3.0 × ULN
	Bicarbonate	mmol/L	< 0.9 × LLN	> 1.1 × ULN
	Bilirubin, total	μmol/L	_	$\geq 1.5 \times ULN$
	Blood urea nitrogen	mmol/L		> 1.5 × ULN
	Calcium	mmol/L	< 0.9 × LLN	> 1.1 × ULN

SAP 3101-301-002 AGN-241689

Table 11–1 Criteria for Potentially Clinically Significant Laboratory Values

			Criteria
Parameter	SI Unit	PCS Low	PCS High
Chloride	mmol/L	$< 0.9 \times LLN$	> 1.1 × ULN
Cholesterol, total	mmol/L		> 1.6 × ULN
Creatinine	μmol/L		> 1.5 × ULN
Creatine kinase	U/L		> 2.0 × ULN
Estimated glomerular filtration rate	$mL/min/1.73m^2$	< 60	_
Glucose, nonfasting	mmol/L	$< 0.8 \times LLN$	> 2.0 × ULN
Lactate dehydrogenase (LDH)	U/L		> 3.0 × ULN
Phosphorus	mmol/L	$< 0.9 \times LLN$	> 1.1 × ULN
Potassium	mmol/L	$< 0.9 \times LLN$	> 1.1 × ULN
Protein, total	g/L	$< 0.9 \times LLN$	> 1.1 × ULN
Sodium	mmol/L	$< 0.9 \times LLN$	> 1.1 × ULN
Triglycerides	mmol/L		> 2.0 × ULN
	μmol/L		> 1.2 × ULN
Basophils, absolute cell count			> 2.0 × ULN
Eosinophils, absolute cell count			> 2.0 × ULN
Hematocrit	Ratio	$< 0.9 \times LLN$	> 1.1 × ULN
Hemoglobin	g/L	$< 0.9 \times LLN$	> 1.1 × ULN

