Lymphocytes, absolute cell count		$< 0.7 \times LLN$	> 1.3 × ULN
Monocytes, absolute cell count		$< 0.5 \times LLN$	> 2.0 × ULN
Neutrophils, absolute cell count		$< 0.7 \times LLN$	> 1.3 × ULN
Platelet count		$< 0.5 \times LLN$	> 1.5 × ULN
Red blood cell count		< 0.9 × LLN	> 1.1 × ULN
White blood cell count	$10^{9}/L$	< 0.9 × LLN	> 1.5 × ULN
рН	рН	< 0.9 × LLN	> 1.1 × ULN
Glucose	_		At least 1+
Protein	_		At least 1+
Specific gravity			> 1.1 × ULN
	Chloride Cholesterol, total Creatinine Creatine kinase Estimated glomerular filtration rate Glucose, nonfasting Lactate dehydrogenase (LDH) Phosphorus Potassium Protein, total Sodium Triglycerides Uric acid Basophils, absolute cell count Eosinophils, absolute cell count Hematocrit Hemoglobin Lymphocytes, absolute cell count Neutrophils, absolute cell count Platelet count Red blood cell count White blood cell count pH Glucose Protein	Chloride mmol/L Cholesterol, total mmol/L Creatinine upmol/L Creatine kinase U/L Estimated glomerular filtration rate mL/min/1.73m² Glucose, nonfasting mmol/L Lactate dehydrogenase (LDH) U/L Phosphorus mmol/L Potassium mmol/L Protein, total g/L Sodium mmol/L Triglycerides mmol/L Uric acid upmol/L Basophils, absolute cell count 10°/L Eosinophils, absolute cell count 10°/L Hematocrit Ratio Hemoglobin g/L Lymphocytes, absolute cell count 10°/L Neutrophils, absolute cell count 10°/L Neutrophils absolute cell count 10°/L Platelet count 10°/L Red blood cell count 10°/L Phyle Blood cell count 10°/L Phyle Glucose —— Protein ——	Parameter SI Unit PCS Low Chloride mmol/L < 0.9 × LLN

LLN = lower limit of normal value; ULN = upper limit of normal value; normal value provided by laboratory.

The number and percentage of participants meeting each of the following criteria for postbaseline hepatic laboratory abnormalities listed in Table 11–2 will be summarized by treatment group. The percentages will be calculated relative to the number of participants with at least 1 available postbaseline assessment. The numerator will be the total number of participants having at least 1 postbaseline value that meets the specific category during the study. A supportive listing will also be provided.

SI = Le Système International d'Unités (International System of Units).

eGFR<60 mL/min/1.73m² indicates moderate eGFR decrease or worse.

Table 11-2 Criteria for Hepatic Laboratory Abnormalities

Laboratory Parameter	Categories
	≥ 1 × ULN
	≥ 1.5 × ULN
	$\geq 2 \times ULN$
ALT	\geq 3 × ULN
	≥ 5 × ULN
	≥ 10 × ULN

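### The only PCS limit for urine specific gravity, 1.1 times the upper limit of normal, is at least 1.10, so the row is expected to read zero in every arm by construction (minor)

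*SAP*

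**What the plan says.** SAP section 11.2 defines the PCS flag by reference to Table 11-1: a laboratory value counts "if they meet either the lower-limit or higher-limit PCS criteria listed in Table 11–1". For urinalysis, the specific-gravity row reads "Specific gravity > 1.1 × ULN" and its low-limit cell is empty, so this is the only route by which specific gravity can be flagged. The table's footnote states "ULN = upper limit of normal value; normal value provided by laboratory"; neither document gives a numerical ULN for this parameter. Protocol Table 6-1 gives the method of measurement: "Urine dipstick for specific gravity, pH, protein, glucose, ketones, bilirubin, and blood".

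The flag feeds a by-arm table: "The number and percentage of participants who have PCS postbaseline clinical laboratory values will be tabulated by treatment group". It also feeds a display of participants with PCS values and a display of their adverse events. SAP section 17.3 says that all post-baseline assessments are used to determine PCS values.

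Two other summaries do not depend on the flag. Descriptive statistics at each timepoint include "Urinalysis: Specific gravity, pH". Shift tables from baseline to the end of double-blind treatment use the categories "low, normal, and high, which are provided by the laboratory vendor".

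**The concern.** A limit set as a multiple of ULN suits a quantity whose scale starts at zero, such as sodium or calcium, which carry the same 1.1 multiplier in Table 11-1. Specific gravity starts at 1.000, and the information lies in the small excess over that value. Adding 10% to the whole number adds at least 0.10, several times the excess at any plausible ULN. Elsewhere the table drops multipliers: eGFR has an absolute limit, and urine glucose and protein have a dipstick grade. Specific gravity does not get that treatment.

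What is at stake is how one row reads. Four zeros in a PCS table look like an observation that nobody had an abnormal value. If the criterion cannot be met, they say nothing about the participants.

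**Working it through.** The plan states no numerical cut-off, so there is no figure to reproduce. The check is arithmetic on the stated rule.

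**Inputs**
- Multiplier 1.1, high side only (SAP Table 11-1).
- ULN supplied by the laboratory, value not given (Table 11-1 footnote). Assumed range: 1.025 to 1.040.
- Specific gravity of water = 1.000, by definition of the quantity.
- Highest attainable urine reading: not in the documents. Assumed range: 1.030 to 1.080.

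**Step 1: lower bound on the cut-off.** Cut-off = 1.1 × ULN. Since ULN ≥ 1.000, cut-off ≥ 1.1 × 1.000 = 1.100. This bound does not depend on which laboratory is used.

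**Step 2: cut-off over the assumed ULN range.** The last column is the excess over water at the cut-off divided by the excess at the ULN, (1.1 × ULN − 1) / (ULN − 1).

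| Assumed ULN | 1.1 × ULN | Ratio of excesses |
|---|---|---|
| 1.025 | 1.1275 | 0.1275 / 0.025 = 5.1 |
| 1.030 | 1.133 | 0.133 / 0.030 = 4.4 |
| 1.040 | 1.144 | 0.144 / 0.040 = 3.6 |

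**Step 3: inverse check.** For a maximum reading M to exceed the cut-off, the ULN must be below M / 1.1.

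| Assumed maximum M | ULN must be below |
|---|---|
| 1.030 | 1.030 / 1.1 = 0.936 |
| 1.050 | 1.050 / 1.1 = 0.955 |
| 1.080 | 1.080 / 1.1 = 0.982 |

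Each of these limits is below water, so no admissible ULN lets the rule fire. Only a reading above 1.10 would change the result.

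**Step 4: two ways the check could mislead.** Reporting on a rescaled unit (1030 instead of 1.030) multiplies the reading and the ULN alike and leaves the comparison unchanged. Table 11-1 is broken in extraction, but the parameter name and its criterion stand on the same row, so misalignment is unlikely.

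**The case against.** The strongest objection is that the documents never state the highest value urine can reach or the range of the dipstick. This stands as a point of evidence: the step is an assumption and is given above as a range. It does not change the result, because everything from 1.030 to 1.080 leads to the same conclusion.

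The second objection is that specific gravity is well covered elsewhere, and this stands too. SAP section 11 includes the maximum among its descriptive statistics, so the highest value per arm and timepoint is shown. The shift tables use the vendor's categories directly. SAP section 17.3 puts all assessments in the listings. Protocol section 6.5.3 has the investigator judge the clinical significance of any value outside the reference range. None of these outputs, however, counts participants with an abnormal value at any post-baseline visit. That is what the PCS row claims to do.

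A reader might infer more than the documents support:
- **That the supportive PCS and adverse-event displays will be empty.** They cover every parameter in Table 11-1; only the contribution from specific gravity is nil.
- **That the rule has 0% sensitivity.** Sensitivity needs a reference definition of a truly significant value, and the plan has none.
- **That a 10% margin on the excess over water was intended.** No text says so.
- **That a safety signal will be hidden.** The adverse events of special interest in Protocol section 6.5.2 concern suicidality and the liver, and the other outputs keep high values visible.

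**Conclusion.** Wrong as written, minor. The bound of 1.10 on the cut-off follows from the definition of specific gravity alone. The conclusion that the row will be zero in all four arms rests also on the assumption that no urine reading exceeds 1.10, which holds throughout the assumed range of maxima. The zero would then carry no information about treatment. The effect is confined to one row of the PCS table and to what specific gravity would add to its supportive displays. Efficacy, power, type I error and the hepatic displays are untouched.

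**What to change.** In Table 11-1, replace the specific-gravity entry with the laboratory vendor's high limit (> ULN), applied to all post-baseline values as SAP section 17.3 already provides. First confirm with the central laboratory that the dipstick can report values above that limit; otherwise one unreachable rule would replace another. If the sponsor does not want the flag, or the reportable range cannot be confirmed, delete the row. Nothing is lost, since the present row is uninformative.

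The cost is one table entry and one line of programming, best done before unblinding. The first option has three side effects:
- Some concentrated-urine values may be flagged, which randomisation should make similar across arms.
- The limit would sit at the ULN, whereas the table's other ULN-based high limits lie above it.
- SAP section 11.2 counts only participants who are not PCS at baseline, so those already above the ULN at baseline would leave the denominator.

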### 9.5.1 Potential Hy's Law Cases

Sites must report every participant who meets the following potential Hy's law criteria if this occurs within the time the participant signs the ICF until 30 days after the last dose of study intervention:

- ALT or AST  $\geq 3$  x ULN **AND**
- Total bilirubin  $\geq 2$  x ULN **AND**
- Alkaline phosphatase  $< 2$  x ULN

Study site personnel must report every participant who meets these criteria. Typically, all 3 analytes will be obtained from the same sample, but they may come from multiple samples taken within a 24-hour period. This requirement applies from the time the participant signs the ICF for the study until 30 days after the final protocol-defined study visit or the last known dose of study intervention (if the final visit does not occur).

A laboratory alert for possible Hy's law cases will be in place, and must notify investigators and Allergan immediately when the above criteria have been met. A possible Hy's law case must be faxed to Allergan on an abnormal liver function reporting form as soon as possible (within 24 hours of learning of the possible Hy's law case) to the fax number on the form or the SAE fax number, even if no AE has occurred. If the event is serious, please complete the SAE form. The eCRF for possible Hy's law cases must be completed within 7 calendar days. Every effort to determine the cause of the liver enzyme abnormalities must be made, and close monitoring should be initiated in conjunction with the medical monitor and medical safety physician and in accordance with the FDA Guidance for Industry, Drug-Induced Liver Injury: Premarketing Clinical Evaluation, July 2009. The participant should return to the study site and be evaluated as soon as possible, preferably within 48 hours from the time the investigator becomes aware of the abnormal results. This evaluation should include laboratory tests, detailed history, and physical assessment.

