	\geq 20 × ULN
	$\geq 1 \times \text{ULN}$
	≥ 1.5 × ULN
	$\geq 2 \times ULN$
AST	\geq 3 × ULN
	≥ 5 × ULN
	≥ 10 × ULN
	≥ 20 × ULN
	≥ 1 × ULN
	≥ 1.5 × ULN
	\geq 2 × ULN
ALT or AST	≥ 3 × ULN
	≥ 5 × ULN
	≥ 10 × ULN
	\geq 20 × ULN
	$\geq 1 \times \text{ULN}$
	≥ 1.5 × ULN
	$\geq 2 \times \text{ULN}$
Bilirubin Total	\geq 3 × ULN
	\geq 5 × ULN
	$\geq 10 \times \text{ULN}$
	$\geq 20 \times \text{ULN}$
	$\geq 1 \times \text{ULN}$
	≥ 1.5 × ULN
	\geq 2 × ULN
Alkaline Phosphatase	\geq 3 × ULN
	≥ 5 × ULN
	≥ 10 × ULN
	≥ 20 × ULN
Concurrent Elevations ¹	ALT or AST \geq 3 × ULN and Bilirubin Total \geq 1.5 × ULN
	ALT or AST $>= 3 \times ULN$ and Bilirubin Total $\geq 2 \times ULN$
Potential Hy's Law ¹	ALT or AST \geq 3 × ULN and Bilirubin Total \geq 2 × ULN and ALP $<$ 2 × ULN
	•

ALT = alanine aminotransferase; AST = aspartate aminotransferase; TBL = total bilirubin; ALP = alkaline phosphatase; ULN = upper limit of normal (value provided by the laboratory).

¹ Elevations are from the same day

[figure not shown]
The number and percentage of participants with an adjudicated case (i.e., $ALT \ge 3 \times ULN$) and/or $AST \ge 3 \times ULN$) will be summarized by treatment group and by relationship of ALT or AST elevation to study medication. The percentages will be calculated relative to the number of participants with at least 1 adjudicated case. The numerator will be the number of participants with at least 1 adjudicated case in the specific category of relationship. If a participant has more than 1 adjudicated case, he or she will be counted in the most relevant category of relationship.

Participants with an adjudicated case (i.e. $ALT \ge 3 \times ULN$ or $AST \ge 3 \times ULN$) will be listed with their ALT and AST assessments, adjudication dates, relationship of ALT or AST elevation to study medication, and confounding factor(s). Additional listings will be provided for participants who meet $ALT \ge 3 \times ULN$ or $AST \ge 3 \times ULN$ and/or potential Hy's law and have one of the following categories: at least 1 abnormal liver biochemistry risk factor, at least 1 liver disease sign and symptom, at least 1 liver diagnostic test performed, consultation with a specialist for liver evaluation, liver lab tests performed, and drug screen performed, respectively. A listing of urine pregnancy test results will be provided for female participants of child-bearing potential with at least one positive result.

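### The potential Hy's law row of SAP Table 11-2 uses a same-day rule, narrower than the 24-hour window that SAP 11.2 and Protocol 9.5.1 give for the same event

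*SAP*

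**What the plan says.** Three places define potential Hy's law with the same three thresholds: ALT or AST at least 3 x ULN, total bilirubin at least 2 x ULN, and alkaline phosphatase below 2 x ULN.

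- **Protocol 9.5.1** sets the site reporting rule: "Typically, all 3 analytes will be obtained from the same sample, but they may come from multiple samples taken within a 24-hour period".
- **SAP 11.2, text** gives the criteria within a 24-hour window, "all based on blood draws collected within a 24-hour period". It then adds a second definition: "Potential Hy's Law criteria without time window is defined by maximum of post baseline elevation of ALT or AST" at the 3 x ULN level, with maximum post-baseline bilirubin at the 2 x ULN level and no alkaline phosphatase condition. It goes on: "Patients who meet the potential Hy's Law criteria from the first dose of study drug to the end of study will be summarized".
- **SAP Table 11-2** has a row labelled "Potential Hy's Law ¹". Footnote 1 reads "Elevations are from the same day". The same footnote marks the rows labelled "Concurrent Elevations ¹", which combine ALT or AST at least 3 x ULN with bilirubin at least 1.5 x ULN or at least 2 x ULN and have no alkaline phosphatase condition.

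Table 11-2 is reported as number and percentage of participants by treatment group, with a supportive listing. SAP Section 19 declares no changes from the protocol's analyses.

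**The concern.** The SAP text names two versions of the event: one with a 24-hour window and one with no window. The Table 11-2 row includes the alkaline phosphatase term, so by content it is the 24-hour version. Its footnote nevertheless gives it a third and narrower window that no text introduces or explains. A programmer following both parts of SAP 11.2 could produce two different numbers for the same named event in the same arm.

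Liver safety is a sensitive topic in this programme. Protocol 1.2 records that ALT increases with telcagepant, an oral drug of the same class, led to development being stopped. Protocol 6.5.2 makes potential Hy's law an adverse event of special interest, and Protocol 3.2 sets up adjudication of ALT and AST elevations. Expected counts are very small, so a difference of one between two displays would be noticed and would need explaining.

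**Working it through.** The plan states no figure on this point, so there is none to reproduce. The check compares the two rules.

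**Inputs.** The window in the Table 11-2 footnote is the same day, read here as the same calendar date. The window in the SAP 11.2 text and in Protocol 9.5.1 is 24 hours. The planned arm size is 218 (Protocol 7.6), and 910 participants were actually randomized (SAP 18.1).

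**Is one rule contained in the other?** Let the first draw be at clock time t (0 ≤ t < 24) and the second g hours later.
- Same-day rule: t + g < 24.
- 24-hour rule: g ≤ 24.

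If t + g < 24 then g < 24, so every same-day pair satisfies the 24-hour rule. A check of all pairs at one-minute steps found 0 exceptions. The converse fails: with t = 20 and g = 12, t + g = 32, so the pair crosses midnight although it is only 12 hours apart. The footnoted row can therefore miss protocol-defined cases but cannot add any.

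**How often would a split pair cross midnight?** This is illustration only.
- If t is uniform over the clock, the share is g/24: 2/24 = 8%, 6/24 = 25%, 12/24 = 50%, 18/24 = 75%.
- If both draws fall between 08:00 and 17:00 on consecutive days, in 15-minute steps, there are 37 x 37 = 1,369 pairs. A pair is within 24 hours when the second clock time is no later than the first, which holds for 37 x 38 / 2 = 703 pairs, and 703/1,369 = 51%. All 703 fail the same-day rule.

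These shares apply only to cases that need two draws to meet the criteria. The documents do not say how common such cases are, so the expected number missed cannot be computed.

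**What would one missed case amount to?** 1/218 = 0.46 percentage points. If the 910 randomized split evenly, 910/4 = 227.5 and 1/227.5 = 0.44 points. The table's actual denominator is participants with at least one available post-baseline assessment, so these figures are approximate.

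**Nesting of the rows.** The concurrent row with bilirubin at least 2 x ULN is the Hy's law row without the alkaline phosphatase term, so under a common window it must contain every Hy's law case. If only the Hy's law row moved to 24 hours, a participant could be counted there and be absent from the broader row.

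**The case against.** The strongest reply is that little depends on this row. ALT, AST, bilirubin and alkaline phosphatase are all in one chemistry panel (Protocol Table 6-1), and Protocol 9.5.1 itself expects a single sample in the typical case. Where two full panels are drawn within 24 hours, the row misses the case only if neither panel meets all three criteria alone. The confirmatory repeat in Protocol 9.5 is at 48 to 72 hours, with panels generally once or twice a week after that, so two draws within 24 hours would usually involve unscheduled testing. Protocol 6.5.3 allows such testing at any time, so the situation is possible but should be rare. All of this stands.

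A reader might infer that a split-draw case would vanish from the study's Hy's law results. The documents do not support that. Such a post-baseline case meets both the 24-hour and the no-window definitions in the SAP 11.2 text, and both are to be summarized. It would also be counted in the single-analyte rows of Table 11-2, which carry no same-day footnote. Site reporting and the laboratory alert follow Protocol 9.5.1 and are untouched.

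A reader might also infer that the concurrent-elevation rows contradict the protocol in the same way. They do not: neither document sets a 24-hour window for those rows, so the same-day rule there conflicts with nothing.

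Finally, same day may have been shorthand for within 24 hours. If so, the footnote should say that, and the edit is the same.

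**Conclusion.** The inconsistency is real and confined to one row. The potential Hy's law count in Table 11-2 can be lower than the SAP's own 24-hour summary of the same event, and it can never be higher. The consequence is two possible counts under one label in a by-arm safety table. No case is lost from the report, and reporting by sites does not change.

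The direction of the error rests on reading same day as the same calendar date. Its size is unknown and probably very small. A difference of 0 versus 1 in a dose arm is possible in this row, but it should not be read as a difference in the trial's overall Hy's law findings. No efficacy, power or type I error figure is affected. Severity: minor.

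**What to change.** On the potential Hy's law row of Table 11-2, replace the same-day footnote with the window already used in the SAP 11.2 text: "all based on blood draws collected within a 24-hour period". State separately which window applies to the concurrent-elevation rows. No passage requires 24 hours there, but using it would keep the bilirubin at least 2 x ULN row a superset of the Hy's law row.

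The cost is one footnote and one programming condition on collection date and time. No new data are needed. The affected counts can only stay the same or rise slightly.
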